20. STATISTICS

20.1. Number of Subjects (approximate)

Approximately 80 subjects will be screened in order to enroll approximately 40 subjects at one (1) site. Discontinued subjects will not be replaced (i.e., their subject numbers will not be reassigned/reused).

The sample size chosen for this study is not based solely on statistical considerations, but was chosen after taking into consideration existing data for approved treatments for AC and the preclinical profile of the drug candidate VSJ-110.

20.2. Study Population Characteristics

Subjects at least 18 years of age, of either gender or any race, who have a positive history of allergic conjunctivitis, and who meet all of the inclusion criteria and none of the exclusion criteria.

20.3. Statistical Methods and Analysis Plan

This section describes the planned statistical analyses in general terms. A complete description of the methodology will be specified in a statistical analysis plan (SAP). Any changes in the statistical methods described in this protocol that occur prior to database lock will be documented in the SAP and will not require a protocol amendment.

20.4. Statistical Hypotheses and Methods of Analysis

Prior to Database lock a Statistical Analysis Plan will be finalized detailing the Efficacy, Safety, and Tolerability analyses that will be performed.

20.4.1. Patient Populations for Analysis

The following analysis populations will be defined for this study:

Intent-to-Treat: will include any subject randomized into the study that receives a dose of study drug and that has completed at least one post-baseline efficacy measurement while on study medication;

Safety: Any subject randomized into the study that receives a dose of study drug;

Per-Protocol: Any subject who is randomized and receives the protocol required study drug exposure and required protocol processing.

Efficacy analyses will be performed on the Intent-to-Treat population and the Per-Protocol population. Safety summaries will be based on Safety set. Subject characteristics will be presented for all subjects randomized.

VP-VSJ-110-2101

Confidential

Vanda Pharmaceuticals Inc.

20.4.2. Patient Disposition

20.4.2.1. Completed Subjects

A completed subject is one who has not been discontinued from the study.

20.4.2.2. Discontinued Subjects

Subjects may be discontinued prior to their completion of the study due to:

- AEs
- protocol violations
- administrative reasons (e.g., inability to continue, lost to follow up)
- manifest clinically active signs of symptoms of allergic conjunctivitis during the ocular and nasal allergic signs and symptoms assessment at Visits 4a, 5a, or 6.
- sponsor termination of study
- COVID-19
- other

Note: In addition, any subject may be discontinued for any sound medical reason.

Notification of a subject discontinuation and the reason for discontinuation will be made to Ora and/or study sponsor and will be clearly documented on the eCRF. Subjects who are discontinued from the study will not be replaced.

20.4.3. Demography and Other Baseline Data

Demographic data and subject characteristics at screening/baseline will be listed and summarized by treatment group for all randomized subjects using descriptive statistics.

Past and current medical history will be summarized by treatment group using the system organ class (SOC) as coded using the Medical Dictionary for Regulatory Activities (MedDRA) coding dictionary.

Past medical conditions will be defined as an onset date prior to randomization and resolved (not on-going). Current medical conditions, defined as an onset date on or after the date of randomization or an onset date prior to randomization and unresolved (on-going), will be reported separately, but similarly to the past medical conditions. If both a past and a current (on-going) medical condition record are indicated for a condition, the condition will be presented under current medical conditions only.

VP-VSJ-110-2101

Confidential

Vanda Pharmaceuticals Inc.

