Screening Period: At Visit 1, subjects will sign the informed consent and an allergic skin test will be performed, if required. At Visit 2, each qualifying subject will undergo a bilateral conjunctival allergen challenge (Ora-CAC[®]) titration using an allergen they had a positive reaction to on their skin test. Subjects who elicit a positive reaction post-CAC will undergo the confirmation CAC at Visit 3 using the same allergen they qualified with at Visit 2.

Treatment Period: Treatment will begin at Visit 4a after subjects are randomized. At this visit, subjects will receive an in-office dose of the treatment they were randomized to receive. Approximately 16 hours post-instillation of study medication, subjects will undergo CAC at Visit 4b. At Visit 5a, subjects will receive an in-office dose of the same study medication. Approximately 8 hours post-instillation of study medication, subjects will undergo CAC at Visit 5b. At Visit 6, subjects will receive an in-office dose of the same study medication approximately 15 minutes prior to CAC. Subjects will receive a final in-office dose of the same study medication at Visit 7 prior to Schirmer's Test and Optical Coherence Tomography (OCT).

Criteria for Evaluation:

Efficacy Measures:

Primary:

- Ocular itching evaluated by the subject at 3(± 1), 5(± 1), and 7(± 1) minutes post-CAC (0-4 scale, allowing half unit increments) at Visits 4b, 5b, and 6.
- Conjunctival redness evaluated by the investigator at 7(± 1), 15(± 1), and 20(± 1) minutes post-CAC (0 to 4 scale) at Visits 4b, 5b, and 6.

Secondary:

The following assessments will occur at 7(± 1), 15(± 1), and 20(± 1) minutes post-CAC (all use a 0 to 4 scale, except eyelid swelling, 0 to 3) at Visits 4b, 5b, and 6:

- Ciliary redness evaluated by the investigator
- Episcleral redness evaluated by the investigator
- Chemosis evaluated by the investigator
- Eyelid swelling evaluated by the subject
- Tearing evaluated by the subject
- Rhinorrhea, nasal pruritus, ear or palate pruritus, and nasal congestion evaluated by the subject

VP-VSJ-110-2101

Confidential

Vanda Pharmaceuticals Inc.

Exploratory:

- Digital Photographs may be taken of all subjects within 10 minutes of the last post-CAC assessment at Visits 3, 4b, 5b, 6.
- Tear meniscus quantitation & replenishment dynamics: Schirmer's Test and OCT at Visit 7.
- Buccal cell samples will be collected at Visit 1 for pharmacogenetic assessments.

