- Pharmacokinetic Measures at pre-dose and 5 minutes(± 2), 15 minutes(± 2), and 30 minutes(± 2) post dose at Visit 4a.

Safety Measures:

- Adverse Events assessed at all office visits
- Visual Acuity at Distance Utilizing an ETDRS chart conducted at Visit 2, 3, 4a, 4b, 5a, 5b, 6, and 7.
- Slit lamp Biomicroscopy conducted at Visit 2, 3, 4a, 4b, 5a, 5b, 6, and 7.
- Intraocular Pressure measured at Visit 1 and Visit 7
- Dilated Fundoscopy measured at Visit 1 and Visit 7

Tolerability Measures:

- Drop comfort assessment (assessed by subjects upon instillation, at 1, and 2 minutes post-instillation) at Visit 4a. Drop descriptor query (assessed at 3 minutes post-instillation) at Visit 4a.

General Statistical Methods and Types of Analyses

For all the analyses, treatment group differences will be tested at a 2-sided significance level of 0.05. The primary statistical analysis will be based on ANOVA model. Categorical variables such as response will be evaluated using Cochran-Mantel-Haenszel (CMH) method or Fisher's exact test. The details of analysis methods will be specified in the SAP.

Summary of Known and Potential Risks and Benefits to Human SubjectsRefer to [Investigator's Brochure \(IB\)](#)

VP-VSJ-110-2101

Confidential

Vanda Pharmaceuticals Inc.

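### Does counting onsets on or after randomisation as current medical conditions spoil the baseline medical-history table?

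*Combined protocol and SAP*

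**What the plan says.** Section 20.4.3 of the protocol is headed "Demography and Other Baseline Data". Its first sentence says that demographic data and "subject characteristics at screening/baseline will be listed and summarized by treatment group", for all randomised subjects. The next paragraph says "Past and current medical history will be summarized by treatment group", using MedDRA system organ class.

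The section then defines two categories. A past condition began before randomisation and has resolved. A current condition can qualify in either of two ways: "Current medical conditions, defined as an onset date on or after the date of randomization", or an earlier onset that has not resolved. The two categories are reported separately. A closing rule says which one prevails: "If both a past and a current (on-going) medical condition record are indicated for a condition", only the current entry is shown.

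Three other places bear on the point:

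- Synopsis, Overall Design: "Treatment will begin at Visit 4a after subjects are randomized".
- Synopsis, Safety Measures: "Adverse Events assessed at all office visits".
- Section 20.3 describes the analyses in general terms and leaves the full method to the SAP: "Any changes in the statistical methods described in this protocol that occur prior to database lock will be documented in the SAP", with no protocol amendment required.

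**The concern.** A by-arm baseline table lets the reader judge whether the groups were alike before treatment. Anything that arises after the first dose may be an effect of treatment and does not belong in it. The first route into the current category appears to let exactly that in, because it sets a lower limit on the onset date and no upper limit.

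It also fits poorly with the rest of its paragraph. It does not require the condition to be ongoing, so one that starts and resolves during the study still counts as current, while the precedence sentence speaks of current conditions as ongoing.

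If such records reached the table, it would mix pre-treatment history with on-study events. The same condition might then be reported once as history and once as an adverse event. With about 20 subjects per arm, even one or two such records would be visible in a row.

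**Working it through.** The plan gives no figure to reproduce. The check is to run the definition over the possible timings and then ask what uses the result.

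**Step 1: classify each timing under Section 20.4.3 as written.**

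| Onset | Status | Category | Baseline information? |
|---|---|---|---|
| Before randomisation | Resolved | Past | Yes |
| Before randomisation | Ongoing | Current | Yes |
| On the randomisation date, before first dose | Either | Current | Yes, arguably |
| After first dose | Ongoing | Current | No |
| After first dose | Resolved | Current by the definition, at odds with the precedence sentence | No |

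Only the last two rows conflict with the section's purpose. In the third row the first route does useful work: if randomisation and first dose fall on the same day, a condition noted that day before dosing has a place to go.

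**Step 2: ask whether the last two rows would be filled.** The definition sorts records that already sit in the medical history. It does not tell the site to enter new conditions there. The Synopsis assesses adverse events at every office visit, including those after dosing begins, so a new condition has an obvious destination elsewhere. The detailed collection rules are not in the text reviewed. Neither misfiling nor double reporting can therefore be confirmed, and neither can be ruled out.

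**Step 3: ask what uses the table.**

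- The Synopsis bases the primary analysis on an ANOVA model and names no medical-history covariate.
- The analysis sets in Section 20.4.1 turn on randomisation, dosing, post-baseline efficacy data and protocol compliance, not on history categories.
- The subgroup examples in Section 20.6 are gender, age and baseline illness severity. That list is open-ended, but it does not name medical history.
- Safety summaries are based on the safety set and do not refer to this classification.

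**Step 4: size.** The number of subjects affected per arm would be 20 × p × f, where p is the share with a new condition after randomisation and f is the share of those filed as medical history. The documents give neither p nor f. If f = 0, the result is 20 × p × 0 = 0 whatever p is. The only figure the documents support is the weight of one subject in a row, 1/20 = 5 percentage points.

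**Step 5: precedence rule.** Suppose a subject has a resolved earlier episode and a later ongoing record of the same condition. The condition is then shown as current only. It moves from one descriptive table to the other, and the subject's history of it is still reported.

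**The case for a change.** The best argument for a change is that it costs almost nothing and cannot hurt. If new on-study conditions are always adverse events, the first route is empty and can go. If they are not, it contaminates the table and must go. Section 20.3 lets the correction be made in the SAP before database lock. Deferral to the SAP is only a partial answer, because Section 20.4.3 states a specific definition that a programmer could carry forward unchanged.

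Part of this stands. The wording is inconsistent, and nothing else in the text reviewed corrects it.

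The dilemma is less clean than it looks, though. The first route is not wholly redundant: deleting it would leave an onset on the randomisation date but before dosing neither past nor current. Nor would deletion settle the remaining ambiguity. The words for resolved and ongoing carry no reference date, so a condition present at randomisation that clears during the study could still be placed in either category. A proper repair would tie both definitions to one time point, which is more than striking a clause, and its only return is a tidier descriptive table.

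The claim of conflict can also be pressed too far. The screening/baseline phrase is attached to demographics and subject characteristics. The medical-history sentence has no time reference of its own, so the conflict rests mainly on the section heading. A stray record would appear in a table labelled current conditions, reported apart from past history.

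**Conclusion.** The drafting slip is real, but it gives no reason to change the plan. Read literally, the definition admits post-randomisation onsets and disagrees with its own precedence sentence. In practice it labels records already held as medical history, for a descriptive summary on which no planned test or efficacy or safety conclusion in the documents depends. An analyst preparing a baseline history table would ordinarily restrict it to conditions present before dosing and leave later onsets to adverse event reporting. Section 20.3 already allows that reading to be recorded in the SAP.

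The size cannot be estimated from the documents and may be zero; one subject in a row is worth 5 percentage points at 20 per arm. The conclusion rests on two assumptions: that new on-study conditions are captured as adverse events, as the Synopsis schedule suggests, and that no later analysis takes the history categories as an input. The wording of the definition is certain. Any practical consequence of it is not shown.

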20.5. Efficacy Data Analysis

20.5.1. Primary Efficacy Variables

The primary efficacy variable is:

- Ocular itching evaluated by the subject at 3(± 1), 5(± 1), and 7(± 1) minutes post-challenge (0-4 scale, allowing half unit increments) at Visits 4b (16 hour duration of action), 5b (8 hour duration of action), and 6 (15 minute onset of action).
- Conjunctival redness evaluated by the investigator at 7(± 1), 15(± 1), and 20(± 1) minutes post-CAC (0 to 4 scale with whole number responses) at Visits 4b (16 hour duration of action), 5b (8 hour duration of action), and 6 (15 minute onset of action).

20.5.2. Secondary Efficacy Variables

Secondary efficacy variables include assessments made on Visits 4b, 5b, and 6, at 7(± 1), 15(± 1), and 20(± 1) minutes post-CAC. All measures use a 0 to 4 scale with whole number responses, except eyelid swelling (0 to 3 scale):

- Ciliary redness evaluated by the investigator
- Episcleral redness evaluated by the investigator
- Chemosis evaluated by the investigator
- Eyelid swelling evaluated by the subject
- Tearing/watery eyes evaluated by the subject
- Rhinorrhea, nasal pruritus, ear or palate pruritus, and nasal congestion evaluated by the subject

20.6. Subgroup Analysis

The subgroup analysis (such as, gender, age, baseline illness severity etc.) for efficacy variables and safety variables may be conducted as described in the SAP.

20.7. Interim Analysis

No interim analyses are planned.

20.8. Deviations in Analysis from Statistical Plan and Other Issues

During the analysis and reporting process, any deviations from the statistical plan designed for this protocol will be described and justified in the final report.
